10.1.4. Analysis of Therapeutic Goals

According to *Wanner et al. 2018*: “*European Expert Consensus Statement on Therapeutic Goals in Fabry Disease*”, eGFR slope can be used to assess renal function in patients with Fabry disease. Based on patients’ pre- switch eGFR slope, the patients will be classified into three kidney disease (KD) severity groups, and the therapeutic goals proposed by the *Wanner et al. 2018* will be assessed respectively based on the pre- and post-switch eGFR slopes as indicated in the table below.

Patients KD Severity Groups	Therapeutic Goals
Stable KD: if pre-switch eGFR slope \geq -3 mL/min/1.73 m ² /year	Achieved if eGFR slope remain in the range of stable KD (i.e. post-switch eGFR slope \geq -3 mL/min/1.73 m ² /year)
Progressing KD: if pre-switch eGFR slope between \geq -5 and $<$ -3 mL/min/1.73 m ² /year	Achieved if response to the treatment (i.e. post-switch eGFR slope become \geq -3 mL/min/1.73 m ² /year)
Fast progressing KD: if pre-switch eGFR slope $<$ -5 mL/min/1.73 m ² /year	Achieved if progression slowdown (i.e. post-switch eGFR slope become \geq -5 mL/min/1.73m ² /year), OR more than 50% decrease in progression (i.e., (pre-switch eGFR slope – post-switch eGFR slope) / pre-switch eGFR slope $>$ 50%)

The number and percentage of patients achieving therapeutic goals (yes / no) for each patient KD group, as well as for all patient groups combined, will be presented.

In addition to examine the therapeutic goals, we’ll also examine the KD status by using the same criteria to classify the patients into the three KD groups based on the post-switch

eGFR slopes, and a shift table will be provided to show the number and percentage of patients from pre-switch to post-switch in their KD status. The percentage will be based on the number of patients in the respective pre-switch KD status.

The number and percentage of patients in each of the KD groups of pre-switch and post-switch will be presented in this shift table as well. The percentage will be based on the total number of patients with KD status determined in the analysis population.

10.2. Cardiac MRI

The left ventricular mass (LVM), and left ventricular ejection fraction (%EF) from cardiac MRI, and the calculated left ventricular mass index (LVMI) indexed to patient's body surface area (g/m^2), will be summarized by descriptive statistics at baseline (prior to infusion in Visit 1), and 12-month visits. The change and percent change from baseline will be summarized as well. The table will be presented overall and by gender.

The left ventricular fibrosis segments will be presented by a shift table from baseline to 12-month visit.

10.3. Plasma Gb3 / Lyso-Gb3 and Urine Lyso-Gb3 Concentrations

Descriptive statistics of plasma Lyso-Gb3 concentration (nM) will be summarized at each visit. The change and percent change from baseline will be summarized as well. The summaries will be presented for the three subgroups in Section 7.4.

The plasma Lyso-Gb3 levels at all visits and the corresponding change and percent change from baseline will be presented in a per subject table. The plasma Lyso-Gb3 levels over time will be presented graphically by a spaghetti plot, for all individual subjects, and for by gender.

In addition, the number and percentage of patients with a reduction from baseline with thresholds of 20%, 30%, 40% and 50% will be summarized at each visit.

Descriptive statistics of plasma Gb3 concentration (nM) will be summarized at each visit and the change and percent change from baseline will be summarized for overall and by the three subgroups in Section 7.4. The change and percent change from baseline will also be presented in the data listing as well.

Descriptive statistics of urine Lyso-Gb3 concentration (pM/mM Creatinine) will be summarized at each visit for overall and the three subgroups in Section 7.4. The change and percent change from baseline will be summarized as well.

10.4. Urine Protein/Creatinine Ratio (UPCR)

UPCR will be classified into four categories. The 1st three are based on the Kidney Disease Improving Global Outcomes (KDIGO) guidelines:

- Normal to mildly increased: if $UPCR < 0.15$ gr/gr,
- Moderately increased: if $UPCR \geq 0.15$ gr/gr and ≤ 0.5 gr/gr, and
- Severely increased: if $UPCR > 0.5$ gr/gr
- PU (Protein Undetectable): in any case that UPCR is reported with a < sign. This happens in any case that the protein level is below the level of detection.

Urine protein/creatinine ratio (UPCR), by spot urine test, will be summarized at each visit based on the above 4 categories (Normal to mild increased; Moderately increased; Severely increased; PU) for overall population and by gender.

The shift of UPCR category from baseline to each of the post-treatment visit will be presented including number and percentage of patients. The percentage will be based on the number of patients in the respective baseline UPCR category.

10.5. Echocardiogram Report

The echocardiography reports were performed by local laboratories, and the evaluations with substantial variations, therefore only data listing will be provided.

Qualitative assessments (normal / other) regarding Aortic, Mitral, Tricuspid, and Pulmonic will be presented by a shift from baseline table will be presented for overall and by gender.

10.6. Stress Test

The quantitative evaluation (yes / no) of symptoms (chest pain, shortness of breath, Dizziness, palpitations, and other) and the overall impression: normal stress test (yes / no) from stress tests will be summarized by descriptive statistics at each visit for overall and by gender.

The shift from baseline will be presented for overall impression: normal stress test (yes / no).

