The sample size of 22 patients is adequate to evaluate the safety of switching from agalsidase alfa to PRX-102 in this orphan disease in which patient recruitment in clinical trials is difficult.

The study endpoints will be evaluated by various summary analyses by study visit and by change from baseline data for each efficacy endpoint. Safety and efficacy endpoints will be compared to baseline using summary statistics. Data will not be analysed by inferential statistics.

An interim analysis may be conducted for administrative purposes.

DOCUMENT APPROVAL

This study will be conducted in compliance with the protocol, Good Clinical Practice (GCP) and applicable regulatory requirements.

SPONSOR REPRESENTATIVE

Signature

____June 6, 2017____

Date

PRINCIPAL INVESTIGATOR

Signature

Date

Print Name: _____

TABLE OF CONTENTS

1. SYNOPSIS.....	2
2. LIST OF ABBREVIATIONS.....	10
3. ETHICAL CONDUCT OF THE STUDY AND REGULATORY REQUIREMENTS	11
3.1 Institutional Review Board (IRB)	11
3.2 Ethical Conduct of the Study	11
3.3 Subject Information and Consent.....	11
4. INTRODUCTION	12
5. STUDY OBJECTIVES.....	15
5.1 Primary Objective	15
5.2 Secondary Objectives.....	16
6. INVESTIGATIONAL PLAN	16
6.1 Overall Study Design and Plan – Description.....	16
6.2 Discussion of Study Design and Choice of Control Group(s)	16
6.3 Selection of Study Population.....	16
6.3.1 Inclusion Criteria	16
6.3.2 Exclusion Criteria	17
6.3.3 Removal of Subjects from Therapy or Assessment.....	18
6.3.4 Replacement Policy	18
7. STUDY PRODUCT.....	18
7.1 Study Medication Supply	18
7.2 Description of Study Product.....	18
7.3 Study drug dosage and preparation	19
7.4 Study Drug Administration.....	19
7.5 Packaging and Labeling	19
7.6 Conditions for Storage and Use	20
7.7 Dispensing, Compliance and Accountability	20
7.8 Prior and Concomitant Therapy	20
8. EFFICACY AND SAFETY ASSESSMENTS.....	21
8.1 Safety Variable(s).....	21
8.1.1 Clinical Laboratory	21
8.2 Efficacy Variables.....	21
8.3 Adverse Events	22
8.3.1 Adverse Events (AE) and Serious Adverse Events (SAE)	22
8.3.2 Procedures for Assessing, Recording, and Reporting Adverse Events and Serious Adverse Events	23
8.3.3 Acute Kidney Injury	24
9. STUDY PROCEDURES AND FLOW CHART.....	25
9.1 Study Visits.....	27
9.1.1 Screening Visit S1 (3 Months \pm 7days before Visit 1)	27
9.1.2 Visits A and B (2 and 1 Month \pm 7 days before Visit 1)	27

9.1.3	Visit 1(± 7 Days).....	28

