8.2 Efficacy Variables

- Mean annualised change in estimated glomerular filtration rate (eGFR_{CKD-EPI}) (See Appendix 6)
- Left Ventricular Mass Index (g/m^2) preferably by MRI (echocardiogram can be used as an alternative) (See Appendix 4)
- Plasma Lyso-Gb3
- Plasma Gb3
- Urine Lyso-Gb3
- Protein/Creatinine ratio spot urine test
- Frequency of pain medication use
- Exercise tolerance (Stress Test)
- Short Form Brief Pain Inventory (BPI) (See Appendix 7)
- Mainz Severity Score Index (MSSI) (See Appendix 5)

-
- Quality of life EQ-5D-5L (See Appendix 9)

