14.2.1.2	Kidney Functions (eGFR and Slope) Per Patient Listing	EP, PP
14.2.1.3.1	Kidney Functions (eGFR Slope) by Baseline eGFR Slope and Baseline eGFR Categories	EP, PP
14.2.1.3.2	Kidney Functions (eGFR Slope) by Baseline UPCR Categories	EP, PP
14.2.1.3.3	Kidney Functions (eGFR Slope) with/without ACEi or ARBs treatment pre-switch	EP, PP
14.2.1.4	Kidney Functions (eGFR Slope) Therapeutic Goal Analysis	EP, PP
14.2.1.5	Kidney Functions (eGFR Slope) by kidney disease Severity Shift from Pre-Switch to Post-Switch	EP, PP
14.2.2.1.1.1	Plasma Lyso-Gb3 Concentrations for Overall and by Gender	EP, PP
14.2.2.1.1.2	Plasma Lyso-Gb3 Concentrations by Baseline FD Classification and Treatment Emergent ADA	EP, PP
14.2.2.1.2	Plasma Lyso-Gb3 Concentrations including Change from Baseline Per Patient Listing	EP, PP
14.2.2.1.3	Number of Subjects with 20%, 30%, 40% and 50% Reduction from Baseline in Plasma Lyso-Gb3 Concentrations for Overall	EP, PP
14.2.2.2.1	Plasma Gb3 Concentrations for Overall and by Gender	EP, PP
14.2.2.2.2	Plasma Gb3 Concentrations by Baseline FD Classification and Treatment Emergent ADA	EP, PP
14.2.2.3.1	Urine Lyso-Gb3 Concentrations for Overall and by Gender	EP, PP
14.2.2.3.2	Urine Lyso-Gb3 Concentrations by Baseline FD Classification and Treatment Emergent ADA	EP, PP
14.2.2.4.1.1	Short Form Brief Pain Inventory (BPI) for Overall and by Gender	EP, PP
14.2.2.4.1.2	Short Form Brief Pain Inventory (BPI) by Baseline FD Classification and Treatment Emergent ADA	EP, PP

Number	Title	Population
14.2.2.4.2	Short Form Brief Pain Inventory (BPI) - Shift from Baseline for Overall	EP, PP
14.2.2.5.1	Cardiac MRI (LVM, LVMi, and %EF) for Overall and by Gender	EP, PP
14.2.2.5.2	Cardiac MRI (Left Ventricular Fibrosis Segments) – Shift from Baseline for Overall	EP, PP
14.2.2.6	Echocardiogram Report – Shift from Baseline for Overall and by Gender	EP, PP
14.2.2.7.1	Stress Test for Overall and by Gender	EP, PP
14.2.2.7.2	Stress Test - Shift from Baseline for Overall and by Gender	EP, PP
14.2.2.8.1	Quality of Life EQ-5D-5L (Overall Health Score) for Overall and by Gender	EP, PP
14.2.2.8.2	Quality of Life EQ-5D-5L (Qualitative Assessments) for Overall and by Gender	EP, PP
14.2.2.8.3	Quality of Life EQ-5D-5L (Qualitative Assessments) - Shift from Baseline for Overall	EP, PP
14.2.2.9.1	Urine Protein/Creatinine Ratio (UPCR) for Overall and by Gender	EP, PP
14.2.2.9.2	Urine Protein/Creatinine Ratio (UPCR) - Shift from Baseline for Overall	EP, PP

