11.3. Data Listings

The following data listings would not be provided if the data listings of the raw data are already provided and suffice per sponsor’s perspective. Data listings will be sorted by the subject ID.

Number	Title
1	Subject Disposition
2	Demographics
3	Concomitant Medications
4.1	Fabry Disease Medical History
4.2	Other Medical History
5	Vital Signs
6	Physical Examination
7.1	Laboratory Test Results – Biochemistry
7.2	Laboratory Test Results – Hematology
7.3	Laboratory Test Results – Anti-PRX-102 Antibodies (IgG)
7.4	Laboratory Test Results – Gb3 Concentration (Plasma GB3 and Plasma Lyso-Gb3)
7.5	Laboratory Test Results – Spot Urine
7.6	Laboratory Test Results – Urinalysis (Dipstick)
7.7	Laboratory Test Results – Coagulation Profile
7.8	Laboratory Test Results – Vitamin D
7.9	Laboratory Test Results – GB3 Concentration (including Urine Lyso-GB3)
8	Electrocardiography (ECG)
9.1	Pre-treatment Adverse Events
9.2	Treatment Emergent Adverse Events
9.3	Fabry Clinical Events
9.4	Infusion Related Events
10	Exposure - Treatment
11.	Findings About - Brain MRI
11.	Findings About - Cardiac MRI
11.	Findings About – Stress Test
11.	Findings About - Echocardiogram
12.	Questionnaires - Brief Pain Inventory (BPI)
12.	Questionnaires – Mainz Severity Score Index (MSSI)
12.	Questionnaires – Quality of Life EQ-5D-5L
13	Protocol Deviations
14	Infusion Premedication
15	Treatment Compliance
16	X-rays
17	Pregnancies

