12. TABLE SHELLS

The table shells are to be provided in a separate document.

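### Exercise tolerance is a named efficacy endpoint, but the SAP tabulates only yes/no stress-test items, so the amount of exercise capacity gained or lost is not summarised

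*SAP*

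**What the plan says.** Protocol 8.2 lists "Exercise tolerance (Stress Test)" among the efficacy variables, and the Synopsis and SAP 3.2.2 carry the same endpoint. None of the three gives a unit or says which stress-test result is meant. The flow charts in Protocol 9 and SAP 4.2 schedule the test at Screening and Visits 1, 14 and 27, without saying what is recorded.

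The Synopsis makes a general commitment: "The study endpoints will be evaluated by various summary analyses by study visit and by change from baseline data for each efficacy endpoint". Protocol 10.5 then gives no analysis for the stress test.

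SAP 10.6 fills the gap. By visit, overall and by gender, it will summarise "The quantitative evaluation (yes / no) of symptoms (chest pain, shortness of breath, Dizziness, palpitations, and other) and the overall impression: normal stress test". For change over time it adds: "The shift from baseline will be presented for overall impression: normal stress test (yes / no)". The table list in SAP 11.1 has two matching entries, "Stress Test for Overall and by Gender" (14.2.2.7.1) and "Stress Test - Shift from Baseline for Overall and by Gender" (14.2.2.7.2). SAP 11.2 has no stress-test figure. SAP 11.3 has a listing, "Findings About – Stress Test", with no description of its fields. SAP 12 says of the shells: "The table shells are to be provided in a separate document".

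**The concern.** Tolerance of exercise is ordinarily a matter of degree: how long, or against what load, a patient can exercise. Symptoms during the test and a judgement that the test was normal are related to it but are different quantities. A patient whose exercise time fell substantially, with no listed symptom and the same overall impression, would contribute no change to either table. So would a patient who improved in the same way.

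What is at stake is interpretation. A shift table with few changes, reported under an endpoint called exercise tolerance, could be taken as evidence that tolerance was stable when nothing in the table measures it. Patients would have undergone repeated stress tests without the named endpoint being estimated.

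The SAP also calls the yes/no items quantitative. This leaves the reader unsure whether a measured quantity was intended and lost, or whether the word is a slip.

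**Working it through.** No figure in the plan needs reproducing; the check sets the passages side by side.

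**Step 1: what is promised.** The endpoint is exercise tolerance (Protocol Synopsis and 8.2; SAP 3.2.2), with by-visit and change-from-baseline summaries for each efficacy endpoint (Protocol Synopsis).

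**Step 2: what is planned (SAP 10.6).**

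| Item | Scale | By-visit summary | Change from baseline |
|---|---|---|---|
| Chest pain | yes/no | yes | no |
| Shortness of breath | yes/no | yes | no |
| Dizziness | yes/no | yes | no |
| Palpitations | yes/no | yes | no |
| Other symptom | yes/no | yes | no |
| Overall impression normal | yes/no | yes | shift table |

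Count: 5 symptoms + 1 impression = 6 variables. All 6 are binary, 0 measure capacity, and 1 of 6 has a within-patient change analysis.

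**Step 3: other outputs.** The stress-test outputs are 2 tables, 0 figures and 1 listing (SAP 11.1 to 11.3). The table titles match SAP 10.6. Neither document names exercise duration, workload or any other graded capacity measure. The listing might hold one, but that cannot be determined from the documents.

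**Step 4: related measures elsewhere.** NYHA class and reduced activity level are scored in the MSSI (Protocol Appendix 5), walking ability in the BPI (Appendix 7) and mobility in the EQ-5D-5L (Appendix 9). These are rated or self-reported limitations belonging to other endpoints, so they do not stand in for performance on a stress test.

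**Step 5: which document governs.** Protocol 10.5 has no stress-test analysis, and SAP 2 says that the SAP prevails over the protocol. The yes/no analysis is therefore the operative one.

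**Step 6: scale of the data.** Tests scheduled: 22 patients × 4 visits = 88. Tests that can contribute a change from the Visit 1 baseline (SAP 7.3): 22 × 2 (Visits 14 and 27) = 44. Both are maxima for the planned number of patients, before any withdrawals. They show how much data is collected, not the size of any bias.

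**Step 7: whether a reason is given.** SAP 10.5 confines most echocardiography output to listings and explains why: local laboratories with substantial variation. SAP 10.6 gives no comparable reason. SAP 9.4 separates quantitative from qualitative ECG items correctly, so the label in SAP 10.6 departs from the SAP's own usage.

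**The case against.** The strongest reply is that the documents never promise a duration or workload. The endpoint is named without a unit, and whether a patient gets through a stress test without symptoms is a coarse but arguable reading of tolerance. On that view SAP 10.6 supplies a definition where the protocol had none. This stands to the extent that the point is a weak operationalisation and not a contradiction between protocol and SAP. It does not remove the mismatch between the endpoint's name and what the tables can show.

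Several stronger readings are tempting and are not supported:

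- A reader might infer that a change in exercise capacity cannot appear in any table. That goes too far. A loss large enough to bring on breathlessness or change the overall impression would show in 14.2.2.7.1 or 14.2.2.7.2. It could not, however, be identified as a capacity change or given a size.
- A reader might infer that the impression is a local reader's opinion. The statement about local laboratories in SAP 10.5 concerns echocardiography only; nobody is named as reading the stress tests.
- A reader might assume that duration or workload sits in existing reports awaiting transcription. The documents do not show that either was recorded.

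Two practical objections also have force. SAP 7.5 says that an interim analysis was done with about 80% of patients completed or discontinued, so a capacity summary added now cannot be presented as pre-specified. Also, no standardised exercise protocol is described, so pooling across sites may not be sensible. Both shape the remedy without removing the need for one.

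Finally, no claim of stable exercise tolerance is made anywhere in the documents. The risk lies in how the result may be read.

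**Conclusion.** The point holds in a limited form. The plan names exercise tolerance as an efficacy endpoint and tabulates only six binary stress-test items, so the amount of capacity gained or lost is not summarised. Such a change could show indirectly, through a symptom or a changed impression, or possibly in the listing.

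The reach is small. This is one of 12 efficacy endpoints in SAP 3.2.2, under the secondary objective and analysed descriptively. The planned paired t-test concerns eGFR slopes (SAP 10.1.3) and is unaffected, as is the primary safety conclusion. The improvement is inexpensive and worth making.

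The conclusion assumes that the separate table shells follow SAP 10.6 and the table titles. If they already include a capacity measure, SAP 10.6 needs only to be brought into line with them. Whether the CRF or stress-test dataset holds such a measure is unknown, and the fix depends on the answer.

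**What to change.** First establish whether the CRF or stress-test dataset already holds a capacity measure, for example exercise duration or peak workload.

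- **If it does:** add to SAP 10.6 its value at each visit and its within-patient change from Visit 1 to Visits 14 and 27, with the number missing and the test protocol used. Label it as an analysis added after the interim analysis, through the documentation route in SAP 2. If test protocols differ too much between sites to pool, give per-patient listings and say why. Keep the symptom and impression tables as supportive.
- **If it does not:** relabel the endpoint in SAP 3.2.2 and 10.6 as stress-test symptoms and overall impression, and draw no conclusion about exercise tolerance from it.
- **In either case:** change the description of the yes/no items in SAP 10.6 from quantitative to qualitative.

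The cost is a little programming and an analysis that is not pre-specified, or else a narrower secondary endpoint. No new tests or visits are needed.

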10.7. Short Form Brief Pain Inventory (BPI)

Descriptive statistics of the qualitative assessments regarding pain severity and pain interference will be summarized at each visit. The change of the assessments will be examined using a shift table from baseline for individual qualitative items and change and percent change from baseline for individual scores and composite scores.

This will be done according to the Brief Pain Inventory User Guide. ([name]). The details are as follows.

Pain severity will be analyzed by each of the four pain severity items (worst, least, average, and right now) respectively and a composite of the four pain severity items (a mean severity score) will be analyzed as well.

Pain interference will be analyzed by each of the seven pain interference items (general activity, mood, walking ability, normal work, relations with others, sleep, and enjoyment of life) respectively, and a composite of the seven pain interference items (a mean interference score) will be analyzed as well. When at least four out of seven interference items for a subject at a visit are available, the mean interference score will be calculated. Otherwise, it will be considered not available (i.e., missing).

BPI summary tables will be presented overall and by the three subgroups in section 7.4.

10.8. Mainz Severity Score Index (MSSI)

Descriptive statistics of the scores, including the change and percent change from baseline, regarding the sign/symptom in general, neurological, cardiovascular, renal dysfunction, and overall score (sum of these four scores) will be summarized at each visit for overall and by gender.

The change of the assessments (scores) will also be examined using a shift table from baseline. Theoretically the range of the scores in general, neurological, and renal dysfunction are from 0 to 18 respectively, 0 to 20 for total cardiovascular score, and 0 to 74 for the overall score. However, majority of the subjects should have the scores in the

middle of the range, especially for the overall score. Therefore, the scores will be categorized in the shift tables, would be < 4, 4-6, 7-9, 10-12, 13-15, and > 15 in six (6) categories for individual scores, and < 11, 11-15, 16-20, 21-25, 26-30, 31-35, 36-40, and > 40 in eight (8) categories for the overall score. Adjustment of the categories might be needed if there were more patients with extreme scores.

10.9. Quality of Life EQ-5D-5L

Descriptive statistics of the qualitative assessments regarding mobility, self-care, usual activities, pain/discomfort, and anxiety/depression will be summarized at each visit for overall and by gender. The change of the assessments will be examined using a shift table from baseline.

The overall health score (from 0 to 100) will be summarized by descriptive statistics at each visit. The change and percent change from baseline will be summarized for overall and by gender.

